5.3 Contraception

During the study, fertile female patients must take precautions to prevent pregnancy since the effects of the study medication on the fetus are unknown. Male patients with partners of childbearing potential must take precautions to prevent pregnancy of the partner since the effects of this drug on sperm are unknown. These restrictions should remain in force for 5 months from the last dose of investigational agent (Nivolumab or ONC201) for WOCBP and for 7 months from the last dose of investigational agent (Nivolumab or ONC201). Drug interaction studies with oral contraceptives have not been performed, so barrier methods of contraception or abstinence should be considered. The definition of effective contraception should be in agreement with local regulation and based on the judgment of the principal investigator or a designated associate. A suggested definition of adequate contraception is the use of double barrier contraception (e.g., condom plus spermicide in combination with a female condom, diaphragm, cervical cap or intrauterine device).

5.4 Inclusion of Women and Minorities

Women and Men of all races and ethnic groups are eligible for this trial.

5.5 Patient Registration

Details of patient's study participation should be documented in clinic/file notes. This project will leverage the Lifespan REDCap instance for making electronic health data accessible for research purposes. REDCap was developed by Vanderbilt University with collaboration from a consortium of institutional partners as a software toolset and workflow methodology for electronic collection and management of research and clinical trial data. The REDCap platform is a secure, web-based application flexible enough to be used for a variety of types of research, provides an intuitive interface for users to enter data, and enforces real time validation rules (with automated data type and range checks) at the time of entry. This platform provides an intuitive data manipulation interface, custom reporting capabilities, audit trail functionality, and real-time data monitoring/querying of participant records. REDCap has multiple data export options to common statistical packages (SPSS, SAS, Stata, R/S-Plus). The investigator will electronically sign the REDCap case reports prior to DSMB review and at the end of follow-up, to indicate that, to his/her knowledge, they are complete and accurate.

All support data must be sent in for registration only. It is the treating physician's responsibility to review all data submitted to the BrUOG Central Office for accuracy and completeness and he/she must electronically sign the off-study form. Sites are to be sure that elements to support

all inclusion and exclusion criteria are submitted and that all assessments from the study procedures calendar (section 8) are submitted for registration.

All patients will be registered through the Brown University Oncology Research Group Central Office. Eligibility Checklist with supporting documentation, and the signed Patient Consent Form must be emailed to the BrUOG Central Office to allow for registration and prior to patient treatment. Registrations should be planned such that the BrUOG office has a full 2 business days to review all registration packets, prior to the scheduled date of treatment (D-7).

6 STUDY TREATMENTS

6.1 Biopsy & Tissue:

There are 3 specimens anticipated for collection, a pre-BrUOG 379 treatment biopsy and a mid-treatment biopsy- both of which are required. If the patient does not progress at time of 2nd biopsy, there is a required 3rd biopsy to occur at time of progression (if patient progresses during treatment/follow-up time period)

All collected specimens will be stored in the laboratory of [name] for correlative testing for future exploratory analyses to assess biomarkers associated with treatment using nivolumab and ONC201 in metastatic colon cancer.

Archival Tissue: All patients must submit representative tissue from their malignancy if it is confirmed there is enough tissue from prior surgery or most recent biopsy. This can consist of archival tumor samples or tissue collected at biopsy to prove recurrence. In both cases, samples should consist of a formalin-fixed paraffin embedded (FFPE) tumor tissue block or at least 20 unstained slides (charged) of 4 uM thickness sent to the lab address located in section 11.1.4. Tissue located outside of Lifespan Cancer Institute hospitals must be confirmed as requested prior to enrollment.

6.2 Treatment Regimen

This is a single arm study with no randomization. All enrolled patients will receive the study drugs.

All patients will receive a dose of ONC201 prior to starting cycle 1, 7 days (-7 days) prior to cycle 1 day 1 and prior to beginning the combination therapy.

Each cycle is 4 weeks long (28 days). Nivolumab: For cycle 1 day 1 in phase Ib and phase II, only a +2 day window is allowed.

Treatment will be administered on an outpatient basis. No investigational or commercial agents or therapies other than those described below may be administered with the intent to treat the participant's malignancy.

The treatment dose of nivolumab is 240 mg. No dose reductions or escalations will be allowed for nivolumab. Dosing delays and modifications are described in Section 6.3-6.5 (DLT, Dosing Delays/Dose Modifications).

The maximum duration of treatment will be 12 months unless it is determined that a patient would derive benefit from continued therapy beyond 12 months, as determined by the investigator. Follow-up for all patients will be approximately 6 months.

The study is expected to be completed over an approximate 3.5-year period

If nivolumab is permanently discontinued due to toxicity, and the patient has had stable or responding disease, then ONC201 may be resumed when toxicity resolves to grade ≤ 1 . If the patient develops recurrent grade ≥ 3 toxicity while on single agent ONC201 after stopping nivolumab then ONC201 will be permanently stopped and the patient removed from protocol treatment.

(The rationale for continuing single agent ONC201 is to gather additional information of the efficacy of ONC201 in colon cancer. As described in section 2.1.2.1 ONC201 has activity in colon cancer cell lines. As described in section 2.2.1, in the phase I study, one patient with metastatic colon cancer that had progressed after multiple lines of standard therapy, had prolonged stable disease with ONC201. Since preliminary studies of ONC201 have demonstrated a promising toxicity profile, it may be helpful to continue ONC201 in stable/responding patients if nivolumab is stopped for immune toxicities.)

If ONC201 is permanently discontinued due to toxicity then nivolumab will be stopped and patients will be removed from study treatment.

When Nivolumab and ONC201 are both due, if administration of nivolumab is delayed based on section 6.6, ONC201 may be given alone, as long as the patient meets criteria for ONC201 dosing. If it is day 1 of a cycle, please also refer to section 6.3.

Nivolumab Description

Page 43 of 145

Protocol- BrUOG 379

CONFIDENTIAL

Dates: 11/04/2018, 11/11/18, 11/16/18, 11/24/18, 11/30/18, 12/2/18, 12/6/18, 12/7/18, 12/10/18, 1/8/19 BMS review, 1/9/19, 1/13/19, 1/15/19, 1/16/19, 1/17/19, 1/20/19, 1/22/19, 2/4/19, 2/19/19, 3/19/19, AM#1 7/22/19, BMS review 8/23/19, AM#2 3/3/20, BMS approved 4/1/20, Oncoceutics approved 4/24/20, AM#3 10/26/2020, BMS approved 1/5/21, Oncoceutics approved 3/30/21

Agent	Premedications; Precautions	Dose	Route	Schedule	Cycle Length=4 weeks
Nivolumab	No premedication or hydration necessary. Subjects should be carefully monitored, as per institutional policy, for infusion reactions during nivolumab administration.	240 mg	IV over approximately 30 minutes	Day 1	Dosing: Q 14 days (2 weeks +/- 2 days) For cycle 1 day 1 a + 2 day window only is allowed

There will be no dose reductions for Nivolumab. All patients should continue to meet treatment parameters required at eligibility, unless as otherwise specified below.

Nivolumab is to be administered as an approximate 30-minute IV infusion. For details on prepared drug storage, preparation, and administration, please refer to the Nivolumab Investigator Brochure (IB). The nivolumab infusion must be promptly followed by a saline flush to clear the line of nivolumab.

Nivolumab injection is to be administered as an IV infusion through a 0.2-micron to 1.2-micron pore size, low-protein binding polyethersulfone membrane in-line filter at 240 mg. It is not to be administered as an IV push or bolus injection. Nivolumab injection can be infused undiluted (10 mg/mL) or diluted with 0.9% Sodium Chloride Injection, USP or 5% Dextrose Injection, USP to protein concentrations as low as 1 mg/mL. Care must be taken to assure sterility of the prepared solution as the product does not contain any antimicrobial preservative or bacteriostatic agent.

ONC201: dose de-escalation will proceed according to a standard 3 + 3 design. Dosing is to be given day 1 of each week and is to occur with Nivolumab dosing when each drug is to be given on the same day. There is a +/- 2-day window.

On days when ONC201 and nivolumab are administered on the same day, ONC201 should be administered within (\leq) 30 minutes **after** completion of nivolumab

If drug cannot be given within the required time-frame, utilizing the window, then the dose is considered missed and is not made up.

All patients will ingest ONC201 capsules in front of research clinical staff during cycle 1.

ONC201 will be taken in front of research staff in cycle 1. Patients are to bring ONC201 drug into clinic day -7, day 1, day 8, day 15, day 22.

Example Phase Ib:

Run-in Day -7: January 7, 2019 ONC201 dose 1

Cycle 1 day 1: January 14, 2019 Nivolumab and ONC201 dose 2 (+ 2-day window allowed, both drugs to be given together)

Cycle 1 week 2: January 21, 2019 ONC201 dose 3 (+/- 2-day window allowed)

Cycle 1 week 3: January 28, 2019 Nivolumab and ONC201 dose 4 (+/- 2-day window allowed, both drugs to be given together)

Cycle 1 week 4: February 4, 2019 ONC201 dose 5 (+/- 2-day window allowed)

End of cycle 1

Dose de-escalation schedule for phase 1b trial ONC201:

Doses in table are exact flat doses. Doses are not adjusted for body weight.

Dose Level	Dose of ONC201* (mg) every week, day 1 (to occur with Nivolumab dosing when both drugs are due)
Level 1 (starting dose level)	625mg
Level 2	500mg
Level 3	375mg

The starting dose schedule of ONC201 will be 625 mg administered once every 1 week, which has been established to be safe in the first-in-human trial in advanced solid tumors (Stein et al, JCO, under review).

Dose limiting Toxicities (DLTs):

DLTs will be assessed in the phase Ib portion of the trial. DLTs will be collected during the run-in (dose 1 of ONC201), cycle 1 and prior to dosing cycle 2 day 1. All patients in a cohort must be assessed for DLTs through pre-dosing cycle 2 day 1 prior to the next cohort being opened.

6.3 New cycle requirements (cycle 2-on) (Refer to sections 6.4, 6.5 and 6.6 before dosing)

A new course of treatment (cycle) with ONC201 and Nivolumab should not begin until the

Page 45 of 145

Protocol- BrUOG 379

CONFIDENTIAL

Dates: 11/04/2018, 11/11/18, 11/16/18, 11/24/18, 11/30/18, 12/2/18, 12/6/18, 12/7/18, 12/10/18, 1/8/19 BMS review, 1/9/19, 1/13/19, 1/15/19, 1/16/19, 1/17/19, 1/20/19, 1/22/19, 2/4/19, 2/19/19, 3/19/19, AM#1 7/22/19, BMS review 8/23/19, AM#2 3/3/20, BMS approved 4/1/20, Oncoceutics approved 4/24/20, AM#3 10/26/2020, BMS approved 1/5/21, Oncoceutics approved 3/30/21

following criteria are met.

- Platelets $\geq 75000/\text{mcl}$
- Granulocytes (ANC) $\geq 1000/\text{mcl}$
- Recovery from other clinically significant, treatment related non-hematologic toxicities to \leq Grade 2

When Nivolumab and ONC201 are both due, if a patient is unable to receive Nivolumab based on section 6.6, ONC201 may be given alone, as long as the patient meets criteria for ONC201 dosing. If it is day 1 of a cycle, please also refer to section 6.3.

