Grade 3	
Hold ONC201
 
Resumption of ONC201 may continue as outlined below:
 
 • First occurrence: Hold ONC201 until \leq Grade 1. Resume ONC201 at one dose frequency cohort lower • Second occurrence: Hold ONC201 until \leq Grade 1. Resume ONC201 at one dose frequency cohort lower with \sim half the number of capsules administered followed by the administration of the other half of the capsules 6-12 hours later • Third occurrence: Off protocol therapy
Grade 4	
 • Off protocol therapy

If, however a patient experiences a “DLT toxicity” after cycle 2 or in the phase II portion it will not be considered a DLT, however: hold treatment (both drugs), once the toxicity reduces to a grade 1 or less, dose reduce (ONC201) and resume treatment, even though it will no longer be defined as a DLT.

On a day when Nivolumab and ONC201 are both due, if a patient is unable to receive Nivolumab based on section 6.6, ONC201 may be given alone, as long as the patient meets criteria for ONC201 dosing. If it is day 1 of a cycle, please also refer to section 6.3.

6.6 Dose delays for Nivolumab Phase Ib and Phase II:

Non-Immune mediated: All clinically significant (grade 3 or higher) hematologic and non-hematologic toxicities felt to have some causality to nivolumab must resolve to \leq grade 2 (excluding weight loss, weight gain, and alopecia) or to baseline prior to a patient receiving a subsequent dose (of Nivolumab). Any dose of nivolumab not administered will be skipped and not made up if outside of the \pm 2-day window.

Immune mediated: Adverse events (both serious and non-serious) associated with nivolumab may represent immunologic etiology.

Nivolumab must be held for suspected immune-mediated toxicities or severe/life-threatening AEs of particular interest as outlined in section below and immune-related toxicities in Appendix D. Please review both Sections (6.6 (below) and Appendix D) prior to infusion of nivolumab in any patient in whom immune-mediated toxicity is suspected.

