- Neurological events (inclusive of neuropathy if not present at baseline) < grade 2
 - Grade 2: Hold until \leq grade 1. If steroids needed, remove from study
 - Grade 3 or 4: remove from study
- Pneumonitis < grade 1
 - Grade 1: Consider delay of treatment, but may proceed with treatment at the discretion of the treating physician.
 - Grade 2: Delay until < grade 1. Consider steroids (see Appendix D, Pulmonary AE Management Algorithm). If not improving after 2 weeks or worsening symptoms, treat as Grade 3 or 4. If improving, taper steroids over at least 1 month once symptoms return to or near baseline and resume protocol treatment.
 - Grade 3 or 4: remove from study
- Creatinine < grade 2
 - Grade 2 and 3: Hold until \leq grade 1. Consider steroid treatment (see Appendix D, Renal AE Management Guideline).
 - Grade 2 or 3 for > 7 days: treat as a grade 4
 - Grade 4: remove from study
- Skin rash (all types) and oral lesions \leq grade 2
 - Grade 3: Hold until \leq grade 1
 - Grade 4: remove from study
- Fatigue \leq grade 2
 - Grade 3: Hold until < grade 2 if within 7 days. If persists >7 days, remove from study.
 - Grade 4: remove from study
- Fever < grade 2
 - Grade 2, 3: hold until \leq grade 1
 - Grade 4: remove from study

6.6.1 Nivolumab Removal from study:

Patients must discontinue nivolumab permanently for the following:

- Any Grade 2 drug-related uveitis or eye pain or blurred vision that does not respond to topical therapy and does not improve to Grade 1 severity within the re-treatment period
OR requires systemic treatment

- Grade 3 drug-related thrombocytopenia > 7 days or associated with bleeding
- Any treatment delay resulting in no nivolumab dosing for > 6 weeks.
- Grade 4 drug-related endocrinopathy adverse events such as adrenal insufficiency, ACTH deficiency, hyper- or hypothyroidism, or glucose intolerance, hypophysitis.
- \geq Grade 3 or 4 hepatic AEs * see appendix D for details
- \geq Grade 4 skin toxicity (per Appendix D can delay or discontinue for grade 3. Must come off, as per this bullet for grade 4 skin)
- ALL OTHER treatment related grade 3/4 treatment related events with the following exceptions:
 - Grade 4 neutropenia \leq 7 days;
 - Grade 4 lymphopenia or leukopenia;
 - isolated Grade 4 electrolyte imbalances/abnormalities that are not associated with clinical sequelae and are corrected with supplementation/appropriate management within 72 hours of their onset;

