6.6.9 Fatigue

Fatigue is the most common adverse event associated with immune checkpoint therapy. Grade 2 or greater fatigue should be evaluated for associated or underlying organ involvement including pituitary, thyroid, hepatic, and/or muscle (CPK) inflammation.

FATIGUE	Management/Next Dose for Nivolumab
Grade 1	Continue protocol therapy
Grade 2	Continue protocol therapy
Grade 3	Hold protocol therapy. Resume protocol therapy if \leq Grade 2 within 7 days.
Grade 4	Discontinue protocol therapy

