6.6.10 Fever

Patients with fever should be evaluated as clinically appropriate. Patients may experience isolated fever during infusion reactions or up to several days after infusion. Evaluation over the course of 1-2 weeks should be done for other autoimmune events that may present as fever.

Fever	Management/Next Dose for Nivolumab
Grade 2	Hold protocol therapy until $<$ grade 1. Then resume protocol therapy
Grade 3	Hold protocol therapy until $<$ grade 1. Then resume protocol therapy
Grade 4	Discontinue protocol therapy

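### Rules for re-dosing or stopping after toxicity contradict each other for grade 3 fatigue, grade 2–3 fever and DLT-type non-hematologic events, and no section is given precedence

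*Combined protocol and SAP*

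**What the plan says.** **New cycles (6.3).** From cycle 2 on, a cycle should not begin until "Recovery from other clinically significant, treatment related non-hematologic toxicities to" grade 2 or less. The heading points to 6.4, 6.5 and 6.6.

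**DLT-type events outside the DLT window or in phase II (6.4.1, repeated in 6.5).** Both drugs are held and, "once the toxicity reduces to a grade 1 or less, dose reduce (ONC201) and resume treatment". Sections 6.4.2 and 16.2.1 say the same in substance.

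**Nivolumab, non-immune events (6.6, opening).** Toxicity of grade 3 or higher with some causality to nivolumab must come down to grade 2 or less, or to baseline, before the next nivolumab dose.

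**Fatigue.** The 6.6 list opens with fatigue of grade 2 or less as the criterion for treatment. Its grade 3 sub-bullet reads "Hold until < grade 2 if within 7 days", with removal from study if the event persists beyond 7 days. The grade 3 row in 6.6.9 reads "Hold protocol therapy. Resume protocol therapy if" grade 2 or less is reached within 7 days.

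**Fever.** The 6.6 list has "Grade 2, 3: hold until" grade 1 or less. For the same grades, 6.6.10 has "Hold protocol therapy until" the fever is below grade 1.

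**Permanent discontinuation (6.6.1).** Nivolumab stops for all other treatment-related grade 3 or 4 events apart from a list of exceptions: certain neutropenia, lymphopenia or leukopenia, electrolyte, hepatic, skin and renal events. Fatigue is not on the list.

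**The concern.** These rules decide whether a patient who has just had significant toxicity is given the drugs again. If two sections give opposite answers for the same event at the same grade, sites will act differently and each can point to protocol text. The first consequence is for patient safety. The second is for the data: exposure, dose holds and discontinuations will partly reflect which section was consulted. With 34 patients planned at the RP2D in a single arm, a few such decisions would show in the safety summaries.

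**Working it through.** No arithmetic applies. The check is to follow three patients through each section that covers them.

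**Patient A: treatment-related grade 3 fatigue, down to grade 2 on day 5.**

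| Section | Result |
|---|---|
| 6.6.9 | Resume |
| 6.6, opening fatigue criterion | Met at grade 2 |
| 6.6, grade 3 sub-bullet | Hold; grade 2 is not below grade 2 |
| 6.6.1 | Nivolumab permanently discontinued; fatigue is not an exception |

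Section 6.6 also disagrees with itself, because its opening criterion and its sub-bullet give different cut-offs.

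**Patient B: grade 2 fever, down to grade 1 when the next dose is due.**

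| Section | Result |
|---|---|
| 6.6 | Resume |
| 6.6.10 | Hold; grade 1 is not below grade 1 |

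A grade 3 fever gives the same split between these two sections.

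**Patient C: phase II; non-immune, clinically significant grade 3 non-hematologic event attributed to nivolumab, now grade 2.** It is outside the nausea, vomiting and diarrhea exception in 6.4.2 and is not an exception in 6.6.1.

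| Section | Result |
|---|---|
| 6.3 | Minimum for a new cycle is met |
| 6.6, opening | Nivolumab recovery condition is met |
| 6.4.1, 6.4.2, 6.5, 16.2.1 | Hold both drugs until grade 1 or less |
| 6.6.1 | Nivolumab permanently discontinued |

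When patient C reaches grade 1, the both-drugs rule says to resume treatment, and 6.6.1 says nivolumab must not be resumed.

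**Does different scope explain the differences?** No. The 6.6 list applies before either drug, to related immune-mediated events. The tables in 6.6.9 and 6.6.10 sit among the immune-related subsections and govern protocol therapy, so both cover an immune-related fatigue or fever. Section 6.6 also tells the investigator to treat a doubtful event as immune mediated until shown otherwise. For patient C, the DLT definition covers events attributed to either drug, so it overlaps the nivolumab-related events in 6.6 and 6.6.1.

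**Is precedence stated?** Not for these events. The authors did state it elsewhere: the hepatic exception in 6.6.1 says that it overrides Appendix D.

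**The case against.** The best defence is that these are minimum conditions to be met together. Section 6.3 says when a cycle should not begin, and it refers onward to 6.4–6.6. A reader might infer that 6.3 by itself permits dosing at grade 2 against the stricter rule in 6.5. The text does not support that: 6.3 can be read as a minimum, and the 6.5 table as a further condition for ONC201-related events in phase II. The opening of 6.6 is also worded as a requirement.

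That defence does not settle the rest. The rows in 6.6.9 and 6.6.10 are instructions to resume, and so is the end of the both-drugs rule. A strictest-rule-wins reading is stated nowhere. Under it, 6.6.1 would leave the 6.6.9 resume instruction with no effect on nivolumab for related grade 3 fatigue.

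A second objection is that the fatigue and fever differences each turn on one sign, below versus at or below, and may be slips. The agreement of the opening fatigue criterion in 6.6 with 6.6.9 makes a slip plausible there. But 6.6 uses both signs within the same list, so they are distinguished as printed, and a site must follow what is printed. The grade 1 limit in the both-drugs rule is written in words.

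A third objection concerns reach, and it stands. The fatigue conflict over the recovery threshold affects patients who improve from grade 3 to exactly grade 2. The fever conflict affects those at exactly grade 1 when a dose is due.

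**Conclusion.** The contradiction is real for three groups: grade 3 fatigue, grade 2–3 fever, and treatment-related, clinically significant, non-immune grade 3 non-hematologic events that meet the DLT-type definition after the DLT window or in phase II. For fatigue and for the third group, the text supports dosing, holding and permanent discontinuation of nivolumab. For fever, 6.6 and 6.6.10 split between dosing and holding.

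Three stronger readings are not supported:

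- A reader might infer that every grade 3 non-immune toxicity is affected. The both-drugs hold covers only DLT-type events. It leaves out, for example, grade 3 thrombocytopenia without bleeding and the nausea, vomiting and diarrhea exception.
- A reader might infer from the fatigue sub-bullet alone that a patient still at grade 2 after 7 days must be removed. That depends on whether persistence means remaining at grade 3 or failing to fall below grade 2. The unambiguous route to stopping nivolumab is 6.6.1.
- A reader might infer from the remark in 6.6.9 that fatigue is the most common event with this drug class that the conflict will arise often. That remark is not about grade 3 fatigue. The documents give no expected rate of grade 3 fatigue or grade 2–3 fever for this combination, so the number of patients affected cannot be estimated.

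The effect is on patient safety, exposure and discontinuation counts. The section 16 boundaries count responses, patients progression-free at 3 months and DLT-type events. None uses a recovery grade, so no design figure changes. The point should be corrected because it bears on safety and costs little. It rests on the signs as printed and on the absence of any precedence statement for these events.

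**What to change.** The clinical team should reconcile 6.3, 6.4.1, 6.4.2, 6.5, 6.6, 6.6.1, 6.6.9, 6.6.10 and 16.2.1 in one table, with a single recovery or discontinuation rule for each drug and event type. The other sections should refer to that table instead of restating thresholds. The protocol should say which text governs if a difference remains, and whether resuming treatment after a both-drugs hold includes nivolumab. Section 6.6.1 must be part of the work; aligning only the recovery grades would leave the conflict between resuming and discontinuing. The choice of thresholds is a clinical decision, and none is proposed here. The cost is a wording amendment, with no change to sample size, analysis or data collection.
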